Title	Survey to evaluate the knowledge and understanding of the key safety messages in the healthcare professional guide and the patient guide for SULIQUA
Protocol version identifier	V6
Date of last version of protocol	22 nd November 2018
EU PAS register number	EUPAS23920
Active substance	Insulin glargine/lixisenatide, ATC code: A10AE54
Medicinal product	SULIQUA (Fixed ratio combination of Insulin glargine ([100 Units/ml]/lixisenatide)
Product reference	Not applicable
Procedure number	EMA/H/C/4243
Marketing authorization holder(s)	Sanofi-Aventis groupe [name]
Joint PASS	No
Research question and objectives	
Research question: Were the key safety messages in the healthcare professional guide and the patient guide, implemented as risk minimisation measures (RMM) beyond routine, effective in:
 
 ○ Providing good knowledge and understanding to health care professionals (HCPs) who prescribed or dispensed SULIQUA and to patients treated with SULIQUA ○ Reducing the risk of medication errors when prescribing/delivering or using SULIQUA 
Objective: To assess the knowledge and understanding of the key safety messages in the health care professional guide and patient guide among HCPs who prescribed or dispensed SULIQUA and patients treated with SULIQUA, respectively

Country(-ies) of study	
Candidate countries: Wave 1 - Czech Republic, Hungary, Slovenia Wave 2 - Belgium, Croatia, Romania, United Kingdom Wave 3 - Countries will be selected based on the product launch and market uptake and the possibility for conducting Wave 3 will be revisited in November 2020 and communicated to PRAC (Pharmacovigilance Risk Assessment Committee) during Wave 2 interim report submission

Author	

IQVIA is a partner centre of the ENCePP scientific network, which is coordinated by the European Medicines Agency. IQVIA is dedicated to excellence in research by adhering to the ENCePP Guide on Methodological Standards and promoting scientific independence and transparency.

Marketing authorization holder(s)

Marketing authorization holder(s)	Sanofi-Aventis groupe [name]
MAH/MAH REPRESENTATIVE contact person	

2 LIST OF ABBREVIATIONS

Abbreviation	Definition
AE	Adverse event
ASOCS	Association of Opinion and Behaviour in Health Field Research Companies
CI	Confidence interval
CSR	Clinical study report
DHPC	Direct Healthcare Professional Communication
EC	Ethics Committee
EM	Educational Materials
EMA	European Medicines Agency
ENCePP	European Network of Centres for Pharmacoepidemiology and Pharmacovigilance.
EphMRA	European Pharmaceutical Marketing Research Association
EU	European Union
GDPR	General Data Protection Regulation
GLP-1	Glucagon-like peptide 1
GP	General Practitioner
GVP	Good pharmacovigilance practices
HCP	Healthcare professional
HMR	Healthcare Market Research
IEC	Independent Ethics Committee
IRB	Institutional Review Board
MAH	Marketing Authorization Holder
LOC	[Sanofi] Local Operating Company
PASS	Post-authorization safety study
PRAC	Pharmacovigilance Risk Assessment Committee
RMM	Risk minimization measures
RMP	Risk management plan
SAE	Serious adverse event
SAS	Statistical analysis software
SAP	Statistical Analysis Plan
SDLC	System Development Life Cycle
SmPC	Summary of product characteristics
SOP	Standard operating procedures
STROBE	Strengthening the reporting of observational studies in epidemiology

4 ABSTRACT

Title

Survey to evaluate the knowledge and understanding of the key safety messages in the healthcare professional guide and the patient guide for SULIQUA

Rationale and background

In the risk management plan (RMP) assessment report by the European Medicines Agency's Pharmacovigilance Risk Assessment Committee (EMA-PRAC), dated 7 July 2016, the Marketing Authorization Holder (MAH) was requested to submit key safety messages for inclusion in a healthcare professional guide and a patient guide to address the potential risk of medication errors occurring at the prescribing, dispensing and patient level. The MAH was further asked to propose a study to assess the effectiveness of these additional risk minimisation measures (RMMs [i.e. the healthcare professional guide and patient guide]). Therefore, this study will evaluate the knowledge and understanding of the educational materials (EM)/guides provided to the health care professionals (HCPs) who prescribed or dispensed SULIQUA and to the patient population treated with SULIQUA after its approval and launch.

Research question and objectives

Research question: Were the key safety messages in the healthcare professional guide and the patient guide, implemented as RMM beyond routine, effective in:

- Providing good knowledge and understanding to HCPs who prescribed or dispensed SULIQUA and to patients treated with SULIQUA
- Reducing the risk of medication errors when prescribing/delivering or using SULIQUA

Objective: To assess the knowledge and understanding of the key safety messages in the health care professional guide and patient guide among HCPs who prescribed or dispensed SULIQUA and patients treated with SULIQUA, respectively.

Study design

The study will be a cross-sectional survey conducted in 3 distinct waves in selected European countries where SULIQUA is marketed (Wave 1: Hungary, Czech Republic, Slovenia, Wave 2: Belgium, Croatia, Romania, United Kingdom, and Wave 3: countries will be selected based on the product launch and market uptake). Croatia is at risk and Italy has been dropped from this study due to challenges related to the ethics committee (EC) approvals. Latvia was planned as a candidate country for Wave 1 but was dropped from the survey due to difficulties to setup the study.

Each wave of the study will correspond to the sequential inclusion of the targeted countries according to the timing of SULIQUA launch and implementation of RMM in these countries. The possibility for conducting Wave 3 will be revisited in November 2020 and communicated to Pharmacovigilance Risk Assessment Committee (PRAC) during Wave 2 interim report submission.

The surveys will be hosted online. In addition, phone (for HCPs) or paper-based questionnaires (for patients) will also be offered as an option for those who have challenges in accessing the internet. The survey questionnaires will comprise multiple-choice and true/false questions. The survey questionnaires were developed jointly by the Sanofi-Aventis Group and IQVIA based on the final approved healthcare professional guide and patient guide and are included as [Annex 2](#) and [Annex 3](#) of

this study protocol. The HCP questionnaire was developed and tested among 6 HCPs for its comprehensibility, consistency and the appropriateness of medical terms. HCPs' comments were implemented in the final version. In addition, a patient/caregiver questionnaire was also tested among 6 non-HCPs for optimal readability by patients.

Population

HCP enrolment

A random sample of at least 150 HCPs prescribing/delivering SULIQUA (general practitioner [GP], endocrinologist/diabetologist, internist, gastroenterologist, nurse, geriatrist and pharmacist) will be recruited per wave, . To minimize selection bias, a database of registered HCPs will be used to randomly enrol HCPs (OneKey, IQVIA). An HCP will only participate in one wave of the survey. All HCPs will provide consent for participation in the survey and data will be anonymous when presented to the MAH.

Patient enrolment:

The target patient population per wave will consist of 150 patients treated with SULIQUA. An invitation letter to participate in the study will be randomly given to patients treated with SULIQUA by the HCP. A patient will only participate in one wave of the survey. There will be no limit on the number of patients recruited per HCP. Patients will provide informed consent and data will be anonymous to IQVIA and to the MAH.

Variables

1. Collected/estimated through HCP questionnaire:

- Information related to HCPs/patients participation: contact rate, response rate, cooperation rate, and refusal rate
- Variables related to HCPs practice information:
 - Duration of practice (years working with diabetic patients)
 - Specialty (GP, endocrinologist/diabetologist, pharmacist, internist, gastroenterologist, nurse, geriatrist)
 - Type of setting (office based, hospital based, both, outpatient pharmacy, hospital pharmacy, diabetes care clinic)
 - Past experience with SULIQUA (number of patients treated with SULIQUA pre-filled pen)
- Variables related to the HCPs knowledge about the prescribing conditions and safety information/warnings of SULIQUA:
 - HCP knowledge about SULIQUA pre-filled pen guide for HCPs
 - Awareness of the responsibility to provide each patient with the guide for patient treated with SULIQUA
 - Knowledge of the instructions for appropriate utilization of SULIQUA pre-filled pen (dose titration, pen choice, storage, adverse reactions)
 - Appropriate labelling of dose range and strength of SULIQUA pre-filled pen and dose steps to be administered in prescription (yes/no)
 - Education/Advice of the patient with regard to dose steps required, design features and appropriate utilization of SULIQUA pre-filled pen, close blood sugar levels monitoring after initiation, safety information)
 - Number of recorded medication errors since EM distribution
- Receipt of SULIQUA pre-filled pen Guide for HCPs (yes/no)
- Distribution to patients/caregivers of the guide for patient treated with SULIQUA (yes/no)

2. Variables collected through the patient questionnaire: patients related variables

- Patients characteristics (age, gender, length of SULIQUA treatment)
- Treating physician (GP, endocrinologist/diabetologist, internist, gastroenterologist, geriatrist)
- Patient knowledge about SULIQUA pre-filled pen guide for patient (yes/no)
- Patient knowledge about SULIQUA pre-filled pen conditions of use (features and appropriate utilisation of SULIQUA pre-filled pen, close blood sugar levels monitoring after initiation, safety information)

Data sources

The survey is a primary data collection conducted through 2 questionnaires administered by web, phone or paper:

- An HCP questionnaire (administered by web or phone)
- A patient questionnaire (administered by web or paper)

Study size

The sample survey will include HCPs from the IQVIA OneKey reference lists.

The sample size calculation is based on the survey objective, i.e. to assess the knowledge and understanding of the key safety messages in the health care professional guide and patient guide among HCPs who prescribed or dispensed SULIQUA and patients treated with SULIQUA, respectively.

Since the expected proportion of HCPs who received and understood the EM related to SULIQUA is not known and there is no evidence supporting it, the worst-case hypothesis will assume a proportion of 50%. The required sample size for the study would be 384 for a precision level of 5%. This sample will be divided into 3 waves, each comprising 128 HCPs and providing a precision of 8.66% for each wave based on the same formula. It is estimated that at least 85% of the questionnaires completed by HCPs will be analysable. Therefore, approximately 450 HCPs shall be surveyed in total. An overall sample of 150 HCPs will be needed for each wave.

Applying the same rule to patients to be recruited, the required sample size would be 150 per wave for a precision level of 8%.

Data analysis

The statistical analysis will be conducted using the statistical analysis software® (SAS) V9.4 on Windows™ (SAS Institute, North Carolina, US).

Results will be presented, overall and at country level per specialty.

Continuous variables will be described by the number of valid cases and missing data, mean, standard deviation, median, Q1, Q3, minimum, and maximum. No missing data will be replaced. Categorical variables will be described as the total number and relative percentage per category. Confidence intervals (CI) of 95% will be calculated when relevant.

Calculations will first be performed on raw data per specialty and weighted according to the real proportion of targeted HCPs in each country to accurately reflect the population the survey seeks to measure.

Possible selection bias will be assessed by comparing the distributions of available characteristics (e.g. region, age, gender, type of practice and specialty) between respondent and non-respondent HCPs.

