5 AMENDMENTS AND UPDATES

DOCUMENT HISTORY

Number	Date	Section of study protocol	Amendment or update	Reason
02	24 February 2020	Refer to protocol amendment summary of changes	Amendment	Refer to protocol amendment summary of changes

AMENDED PROTOCOL 02 (24 FEBRUARY 2019)

This amended protocol (amendment 02) is considered to be substantial based on the criteria set forth in Article 10(a) of Directive 2001/20/EC of the European Parliament and the Council of the European Union. This is because the actual launch schedules and the utilization of SULIQUA in the European Union (EU) are different from the previous projections utilized for the clinical conduct and timelines of the previous version of the submitted study protocol.

OVERALL RATIONALE FOR THE AMENDMENT

The SULIQUA launches in EU have started in the second quarter of 2018, and only in a few countries (list provided in Table 2 of protocol). In some countries, e.g. Sweden and Finland, only one of the two available pre-filled pens have been launched. Therefore, in these countries there is no need to distribute the healthcare professional guide or the patient guide, which addresses the potential risk of medication errors due availability of two pens. SULIQUA has not yet been launched in some of the major EU countries such as France, Germany and Spain. In summary, in EU, the utilization of SULIQUA has been much lower than projected.

Considering the actual launch and utilization of SULIQUA, the MAH plans to amend the study protocol on conducting and reporting this survey according to the rational summarized in the table below, and in line with the following plan:

- Recruitment for Wave 1 started in September 2019
- No limit on the number of patients recruited per HCP i.e. all patients an HCP can recruit will be included in this study
- Questionnaire collection is extended to 6 months

Section # and Name	Description of Change	Brief Rationale

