8 RESEARCH QUESTION AND OBJECTIVES

The research questions for this study is: Were the key safety messages in the healthcare professional guide and the patient guide, implemented as risk minimisation measures (RMM) beyond routine, effective in:

- Providing a good knowledge and understanding to health care professionals (HCPs) who prescribed or dispensed SULIQUA and to patients treated with SULIQUA
- Reducing the risk of medication errors when prescribing/delivering or using SULIQUA

The main objective of this study is to assess the knowledge and understanding of the key safety messages in the healthcare professional guide and patient guide among HCPs who prescribed or dispensed SULIQUA and patients treated with SULIQUA, respectively.

Specific objectives are to assess the proportion of:

- HCPs:
 - Who receive, understand and implement the safety messages conveyed by EM for SULIQUA
 - Who are aware that prescriptions for SULIQUA should state clearly the dose range and strength of SULIQUA in a pre-filled pen and the number of dose steps to be administered by the patient
 - Who advise patients with regard to dose steps required, design, features and appropriate utilization of SULIQUA pre-filled pen, close monitoring of blood sugar levels after initiation, and anticipated adverse reactions
 - Who noted medication errors in treated patients
- Patients/caregivers
 - Who acknowledge receiving SULIQUA pre-filled pen guide for patients and caregivers
 - Who read the patient guide before using SULIQUA pre-filled pen
 - Who implemented the safe utilisation of SULIQUA according to safety information for the SULIQUA pre-filled pen
 - Who were trained/advised by their HCP (physician or pharmacist) on how to use SULIQUA pre-filled pen

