9.2 SETTING

The survey will be conducted in selected European countries in 3 waves. Each wave will correspond to the sequential inclusion of the targeted countries according to the timing of SULIQUA launch and implementation of RMM in these countries. Furthermore, the selection of countries to be involved in each wave of the survey will take into account the following criteria:

- Where SULIQUA has been registered and both pens were marketed for at least 6 months at the start of the survey (Table 2)
- Where the HCPs have been targeted for the EM and direct healthcare professional communication (DHPC) at the start of the survey
- where SULIQUA availability and market penetration is sufficiently high to allow HCPs participation

The MAH will therefore take into account the predicted market uptake to preselect the countries and will ensure that the study will be performed in countries where SULIQUA (both pens) is available and accessible to patients. The exact list of participating countries is currently being refined.

Table 2, below, shows the provisional timetable for commercial launch of SULIQUA in selected European countries. Dates are projections and may be subject to change during the course of the study. The list of countries participating in each wave will be finalized before each wave starts according to the effective launch date.

Table 2: List of candidate countries to be included in the successive waves according to SULIQUA provisional dates when both pens were made available to patients in EU (source Sanofi-Aventis Group)

Country	Available to patients (both pens)	Wave		
		1	2	3*
Hungary	09 October 2017	X	-	
Czech Republic	02 May 2018	X	-	
Slovenia	01 June 2018	X	-	To be determined
Romania	05 June 2018 (peach pen) 23 April 2019 (olive pen)	-	X	
Croatia	Q3 2019	-	X	
Belgium	01 November 2018	-	X	
United Kingdom	10 May 2019 (olive) 17 May 2019 (peach)	-	X	

X refers to candidate to be included in the present wave

*The details on countries will be updated if Wave 3 is deemed feasible at the time of Wave 2 report submission.

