Essentially, countries selected will be different from one wave to the next wave based on the actual market penetration and product availability to patients. Croatia is at risk and Italy has been dropped from this study due to challenges related to the ethics committee (EC) approvals. Latvia was planned as a candidate country for Wave 1 but was dropped from the survey due to difficulties to setup the study. Wave 3 countries are yet to be determined, and for this the MAH will continue monitoring which additional countries can be added and provide an update on the sales data (i.e. product launch and market uptake) in the interim reports.

The first wave of survey includes the countries in which EM were distributed from the end of Q4 2017. A total of 150 HCPs and 150 patients/caregivers will be included in Wave 1.

The second wave of the survey will include countries in which EM were distributed from Q3 2018. A total of 150 HCPs and 150 patients/caregivers will be included in Wave 2. If the sample size is difficult to reach, the countries in which EM were distributed in a following quarter, i.e. Q3-Q4 2019 but which were not included in Wave 1, will be included in Wave 2.

The third wave of the survey will include countries in which EM will be distributed from Q3 2019. A total of 150 HCPs and 150 patients/caregivers will be included in Wave 3. If the sample size is difficult to reach, the countries in which EM were distributed earlier will be included in Wave 3.

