9.2.2 Eligibility criteria

9.2.2.1 Inclusion criteria

The HCP survey will be conducted among HCPs meeting the following inclusion criteria:

- HCPs who prescribe/deliver SULIQUA

The patient survey will be conducted among patients (or their caregivers) meeting the following inclusion criteria:

- Respondents (patients or caregivers of a patient) who receive SULIQUA

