9.2.2.2 Exclusion criteria

HCP survey

The following exclusion criteria will be checked at the beginning of the web questionnaire:

- HCPs who are not involved in patient treatment
- HCPs who may have conflicts of interest with the survey (i.e. HCPs employed by regulatory bodies, pharmaceutical industries)
- HCPs who have participated in the previous waves of the survey
- HCPs who have already 2 or more colleagues participating in the survey from the same practice in the same wave

Patient survey

The following exclusion criteria will be checked at the beginning of the web questionnaire:

- Patients (or caregivers) who may have conflicts of interest with the survey
- Patients (or caregivers) who have participated in the previous waves of the survey

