1	The dose pointer of the pen shows the number of dose steps to be injected	()	()
2	1 dose step of Suliqua contains 1 unit of insulin glargine 100U/ml plus a corresponding amount of lixisenatide	()	()
3	Even when the needle is changed, the pen should not be used by another person	()	()
4	You cannot use a syringe to withdraw Suliqua from a pre-filled pen	()	()
5	It is important to closely monitor your blood sugar level when starting Suliqua	()	()
6	One dose step of Suliqua only states the amount of lixisenatide	()	()

Data: single punch per row

Answer: Option 6 is false.

Q4. According to your knowledge, which of the following statements are true and which are false?
 Please select one answer per row.

		TRUE	FALSE
1	The prescription should mention which pre -filled pen you should use	()	()
2	The Suliqua (10-40) pen allows a daily injection of doses between 10 and 40 dose steps	()	()
3	The Suliqua (30-60) pen allows a daily injection of doses between 30 and 60 dose steps	()	()
4	If my total daily dose is more than 60 dose steps, then I should not use any of the Suliqua pens	()	()

Data: single punch per row

If S4=1 then skip item 3

If S4=2 then skip item 2

If S4= 3 then keep item 2 and item 3

Answer: All is true

Q5. Have you - or has the person you take care of - received the Suliqua Patient Guide from your physician or pharmacist? Please select one answer

Yes No

Data: single punch

Q6. Have you - or has the person you take care of - read the following educational materials (EM) related to Suliqua before using Suliqua? Please select one answer per row.

1	Suliqua Patient Guide (information that you may have received from your physician or pharmacist)	 Yes  No
2	Patient Information Leaflet (information available in each pack of Suliqua pre-filled pen)	 Yes  No

Data: single punch per row

If Q5=2 then skip item 1

Q7. Where would you - or the person you take care of - look for additional information if you have difficulties in understanding the prescription or use of the Suliqua pen ? You can select more than one answer.

	Prescription/ missing information	
1	Ask a physician	()
2	Ask a pharmacist	()
3	Ask a nurse	()
4	Read the Information Leaflet from the Suliqua package	()
5	Read the Suliqua Patient Guide	()
6	Read on the web	()

Data: multiple punch
If Q5=2 then skip item 5

Answer: all is true

Note :

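### Patients are eligible whatever their treatment start, so some who began before the guide reached their country can only answer No to having read it before use, and no planned analysis separates them

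*Protocol*

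**What the plan says.** The abstract (Protocol section 4, patient enrolment) states: "The target patient population per wave will consist of 150 patients treated with SULIQUA". Inclusion criteria (Protocol 9.2.2.1) ask only for "Respondents (patients or caregivers of a patient) who receive SULIQUA". The exclusions (9.2.2.2) are a conflict of interest and earlier participation: "Patients (or caregivers) who have participated in the previous waves of the survey". None of these sections limits when treatment began.

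Section 8 lists, among the patient proportions to be estimated, those "Who read the patient guide before using SULIQUA pre-filled pen". Annex 3 puts this as Q6, which asks whether the respondent has "read the following educational materials (EM) related to Suliqua before using Suliqua". Item 1 is the patient guide and item 2 the package leaflet. Item 1 is skipped if Q5 (guide received) is No.

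Q6 and Q7 form patient success factor 3, which needs 6 of 8 sub-questions (9.7.1). Q5 alone is factor 1. The measures count as effective for patients if at least 2 of the 3 proportions reach 80%.

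On timing, 9.2 says of Wave 1: "The first wave of survey includes the countries in which EM were distributed from the end of Q4 2017". For Wave 2 it gives Q3 2018. Both statements are made per wave. Table 2 shows both pens available in Hungary on 9 October 2017. In Romania the peach pen came on 5 June 2018 and the olive pen on 23 April 2019. Section 5 says of countries with only one pen that "in these countries there is no need to distribute the healthcare professional guide or the patient guide".

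Length of treatment is collected (9.3.2; Annex 3, S3, with a top band of over 12 months). It is absent from the patient stratifiers in 9.7 (country and treating physician's specialty) and from the patient profile variables in 9.7.1.

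**The concern.** The objective depends on the order of two events, reading the guide and first use. Eligibility does not. A patient who began treatment before any guide existed in the country, and was given one afterwards, answers No to Q6 item 1 by construction. That answer says nothing about whether patients who could have read the guide first did so.

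At stake is the proportion for a named objective. It would be lowered by an amount that depends on each country's launch and distribution history. Section 9.7.2 presents success by country, so a difference between countries could reflect launch sequence rather than use of the guide.

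**Working it through.** **1. The plan's own figure.** With P = 0.5, z = 1.96 and e = 0.08, n = P(1-P)z²/e² = 0.25 × 3.8415 / 0.0064 = 150.06. The stated 150 per wave is reproduced.

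**2. Who is affected.** There are two kinds of patient who started before distribution.
- Received the guide later: Q5 is Yes, Q6 item 1 is asked, and the answer must be No.
- Never received it: Q5 is No and Q6 item 1 is skipped. Section 9.7 leaves missing values out of denominators, so, if a skipped item is treated as missing, this patient does not enter the read-before-use proportion. The patient counts under factor 1 as true non-receipt.

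Only the first kind distorts read-before-use.

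**3. Effect on the proportion.** Let s be the share of late-guide starters among those asked item 1, and r the true rate among the others. The observed proportion is r(1-s). With r = 90% (assumed), it is 85.5%, 81% and 72% at s = 5%, 10% and 20%.

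**4. How large the early-start share could be in Romania.** Assumptions: no discontinuation; survey at mid-Wave 2, 16 April 2020, the midpoint of the dates in section 6, which is 681 days after the peach pen; starts either uniform over time (share = gap/681) or rising linearly (that share squared); Romania a quarter of 150, about 38 patients. The points are out of 150, so all 150 are taken as asked item 1. They also assume that every early starter later received the guide and would otherwise have read it first.

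| Guide distributed in Romania from | Gap (days) | Share, uniform / rising | Points of Wave 2 proportion |
|---|---|---|---|
| 1 July 2018 (start of Q3 2018) | 26 | 3.8% / 0.15% | 1.0 / 0.04 |
| 30 September 2018 (end of Q3 2018) | 117 | 17.2% / 3.0% | 4.4 / 0.7 |
| 1 January 2019 (earliest date meeting the 6-to-12-month aim in 9.6.1 when Wave 2 opens 1 January 2020) | 210 | 30.8% / 9.5% | 7.8 / 2.4 |
| 23 April 2019 (second pen) | 322 | 47.3% / 22.4% | 12.0 / 5.7 |

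Example for the last row: 0.473 × 38 = 18.0 patients, and 18.0/150 = 12.0 points; 0.224 × 38 = 8.5 patients, and 8.5/150 = 5.7 points.

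**5. Hungary.** From 9 October to 31 December 2017 is 83 days. To mid-Wave 1 (15 January 2020) is 828 days. The share is 83/828 = 10.0% if uniform and 1.0% if rising.

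**6. Factor 3.** Assume independent items, each answered appropriately with probability p. With all 8 items open, P(at least 6) is 89.5% at p = 0.85 and 96.2% at p = 0.90. A late-guide patient needs 6 of the other 7: 71.7% and 85.0%. With s = 20% of the wave, the factor 3 proportion is 0.8 × 89.5 + 0.2 × 71.7 = 85.9% at p = 0.85, and 0.8 × 96.2 + 0.2 × 85.0 = 94.0% at p = 0.90. The loss is about 2 to 4 points and does not cross 80% here.

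**7. What S3 can resolve.** At mid-Wave 1, Hungarian starters before 15 January 2019 all fall in the top band: 463 of 828 days, or 56% if uniform. S3 cannot place them relative to the end of 2017. In Romania at mid-Wave 2, the edge of the top band falls at about 16 April 2019, a week before the second pen. The existing bands therefore separate early starters fairly well if distribution began then, and poorly if it began in 2018.

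**The case against.** The strongest reply is that little of this reaches the success rule. Patients who never received the guide skip Q6 item 1. One No does not fail factor 3, which tolerates two. Factor 2 does not depend on when the guide was read, and only 2 of 3 factors are needed. All of that stands.

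A reader might infer that factor 1 is biased too. The documents do not support this. Q5 has no before-use condition, and the stated population is patients treated with SULIQUA, so a current user never given the guide is a real coverage gap. A reader might also infer that the guide's effect is understated. There is no comparator and so no effect estimate to understate.

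The long Romanian gap is an inference. Section 5 names Sweden and Finland as its one-pen examples, while 9.2 gives Q3 2018 for Wave 2 as a whole. Table 2 lists availability, calls its dates projections, and does not show treatment starts. The dates therefore permit such patients; they do not prove that any were enrolled. This stands, and it is why the range begins near zero.

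Finally, a split by a collected item could be left to the statistical analysis plan. That stands only in part: 9.7 and 9.7.1 name the stratifiers and profile variables and leave out the one this objective needs. The aim in 9.6.1 of surveying 6 to 12 months after distribution governs fieldwork, not individual treatment starts.

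**Conclusion.** The point holds for the read-before-use objective and, more weakly, for factor 3. Eligibility ignores treatment start, the measure depends on it, the protocol's dates leave a window before distribution in Hungary and Romania, and no listed analysis uses treatment length to separate those patients. The direction for read-before-use is clear: downwards, wherever late-guide starters are enrolled.

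The size is not known. For Romania it is about 0-1 point of the Wave 2 proportion if the guide was distributed from 1 July 2018, and 6-12 points if not until 23 April 2019. The upper figures rest on all the assumptions in step 4 together. A reader might take them as the expected bias, or conclude that the effectiveness verdict would change. Neither follows from the documents.

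**What to change.** In 9.7.1, keep factors 1 to 3 on all patients, so that the target population does not change. Add:
- Q6 item 1, and factor 3 as a sensitivity analysis, among patients whose S3 band places the start after their country's distribution date, using the sponsor's own dates;
- separate rows for earlier starters and for patients whom S3 cannot classify;
- Q5 by S3 band, descriptively.

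For fieldwork not yet open, split the over-12-months band or ask month and year of first use.

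The cost is a subgroup definition and a smaller denominator. If 120 of 150 remain, the half-width at P = 0.5 is 1.96 × √(0.25/120) = 8.9% instead of 8.0%. In Wave 1 countries many long-term users will stay unclassified, which the separate row makes visible.
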